9.3.2 Secondary Hypothesis

There is no secondary hypothesis.

9.3.3 Exploratory Hypotheses

9.3.3.1 Relationships between performance and test battery outcome

H1: The hypothesis is that there is a significant difference between:

H0: The hypothesis is that there is no significant difference between:

- 1) Sentence scores in quiet at 1-day
- 2) Sentence scores in 10 dB SNR at 1-month
- 3) SSQ12 scores

For pass versus fail groups from the test battery.

9.3.3.2 Value of classification criterion as good/poor performer

Receiver-operating characteristic analysis techniques will be applied to determine if the strength of the relationship between binary performance threshold score criterion (good vs poor) and pass/fail test-battery outcome can be increased.

9.3.3.3 Relationship between demographic and hearing-characteristics and pass/fail on processing parameter tests

H1: The hypothesis is that there is a significant relationship between duration of deafness/congenital hearing loss and:

H0: The hypothesis is that there is no significant relationship between duration of deafness/congenital hearing loss and:

- 1) The phonological processing test score.
- 2) The percent difference in slopes between negative and positive leading phase ECAP amplitude growth.
- 3) The width of the ECAP SOE functions.

9.3.3.4 Relationship between subjective hearing performance and sentence recognition threshold in noise

H1: The hypothesis is that there is a significant relationship between SSQ12 score and SNR50 for sentence recognition in noise.

H0: The hypothesis is that there is no significant relationship between SSQ12 score and SNR50 for sentence recognition in noise.

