Finally, the good/poor criterion could be explored: Like the arbitrary 60/100 at 1-day criterion in Figure 2, the switching point for good/poor can be tuned using receiver-operating curve techniques to provide the highest level of categorical certainty based on the processing test outcomes.

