6.2 Exploratory Objectives

- Evaluate the correlation of testable parameters with sentence score at 1-day in quiet and at 1-month in noise.
- Evaluate the correlation of testable parameters, sentence scores and self-reported performance (SSQ12) at time of non-opposition.
- Determine whether shifting the good/poor performer 90% cut-off score would improve the correlation with pass/fail on the parameter tests.
- Explore the relationships between testable parameters measured post-implantation and demographic and hearing-related factors.

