9 STATISTICAL CONSIDERATIONS

9.1 General Considerations

Descriptive statistics will be derived for all data points. All analyses will be made on the full data set. All analyses will be presented as aggregated data without the possibility of identifying data from individual subjects.

Sentence recognition scores form the basis for most study endpoints. Missing test scores will be resolved with the study team. For example, if subjects can be assumed to have scored zero at 1-day or 1-month.

For the secondary endpoints such as longitudinal sentence test scores, logarithmic interpolation can be used for data missing for any given time-point. For missing fixed SNRs, logistic interpolation from present SNRs will be used. Longitudinal data for all subjects will be fit to the standard 1-day, 1-month, 3-month, 6-month, 1-year, 2-year, 3-year follow-up schema, with scores in quiet and 10 dB, 5 dB, 2 dB and 0 dB SNR. (NB certain levels are often omitted in standard clinical testing where the subject is known to be performing at ceiling or at floor for the condition.)

There is no criterion for termination of the study on statistical grounds.

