9.4 Sample Size Determination

Two scenarios with different underlying good/poor performer proportions were simulated (see figures 3 and 4): 50/50 and 40/60. $\geq 80\%$ power is obtained under both scenarios. Higher specificity and sensitivity would increase the power. Increasing the total number of subjects would also increase power.

[figure not shown]

Figure 4: Power calculations for a 40%/60% good/poor performer scenario.

Based on sample size calculations, a total of 30 eligible subjects are required to provide $>80\%$ power to reject the null hypothesis for the statistical test for the primary objective.

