9.5 Analysis Population

There are no sub-populations.

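### Section 9.3.3.2 chooses the best good/poor cut-off and measures its gain over 90 on the same subjects (about 30), so the reported gain is biased upward

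*Combined protocol and SAP*

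**What the plan says.** Section 6.2 lists this exploratory objective: "Determine whether shifting the good/poor performer 90% cut-off score would improve the correlation with pass/fail on the parameter tests". Section 9.3.3.2 gives the method, receiver-operating characteristic techniques, used to "determine if the strength of the relationship between binary performance threshold score criterion (good vs poor) and pass/fail test-battery outcome can be increased". Section 4.3 describes how the cut-off would be chosen: "the switching point for good/poor can be tuned using receiver-operating curve techniques to provide the highest level of categorical certainty", judged against the processing-test results.

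On the data to be used, section 9.1 states: "All analyses will be made on the full data set". Section 9.5 adds: "There are no sub-populations". On size, section 9.4 states that "a total of 30 eligible subjects are required to provide" more than 80% power for the primary test.

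No section names the association metric, the candidate cut-offs, a minimum gain, an interval for the gain, a resampling correction or a second sample. Section 9.3.3.2 has no null and alternative hypothesis, unlike 9.3.3.1, 9.3.3.3 and 9.3.3.4. Section 9.8 covers group comparisons and correlations only.

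**The concern.** The objective is a comparison: is some other cut-off better than 90? The method takes the cut-off with the strongest association in the sample and compares it with 90 in that same sample. The winner is partly chosen for its favourable sampling error, so its observed advantage overstates its real one. With about 30 subjects that error is large.

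What is at stake is the answer to one of four listed exploratory objectives. A reader given only the tuned cut-off and its association could not tell a real improvement from the product of the search. Section 4.3 itself calls the 90 criterion open to debate, so an apparently better alternative would attract attention.

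**Working it through.** **Inputs from the documents.** N = 30 (9.4). Sensitivity and specificity about 80% (7.2.3). Good/poor splits 50/50 and 40/60 (9.4). Expected share reaching 90: 30–50% (4.2.2). Scores are out of 100, one list per condition (7.3.3.6). Chi-squared test at 0.05 (9.3.1).

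**Assumptions.** The documents' text does not describe the distribution of scores below 90, and Figure 2 is not shown, so a shape was assumed. The metric was phi between score at or above the cut-off and battery pass. Candidate grids were varied because the plan fixes none.

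**Step 1: the plan's own figure.** The plan states at least 80% power for the primary test. Comparing 80% with 20% battery failure by exact enumeration of the 2×2 table gives:
- 50/50 split (15 and 15): 94.1% for uncorrected chi-squared, 87.2% for Fisher.
- 40/60 split (12 and 18): 93.9% and 88.5%.

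The plan's statement is reproduced. At 50/50 the expected table is 12, 3, 3, 12, so phi = (12×12 − 3×3)/(15×15) = 135/225 = 0.60.

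**Step 2: the sign of the gain.** Apparent gain = max over c of phi(c), minus phi(90). With 90 among the candidates, the maximum is at least phi(90), so the gain is zero or more in every sample. This needs no distributional assumption.

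**Step 3: how often another cut-off beats 90 (simulation, N = 30, phi).**

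| Cut-offs searched | No association | 90 truly best, 80/80 |
|---|---|---|
| 1 to 100, step 1 | about 97% | 48–50% |
| 10 to 100, step 5 (19 cut-offs) | 92–93% | 27–39% |
| 7 cut-offs, at least 5 subjects per group | 79–84% | 26–28% |
| 80, 90, 95 | 67–73% | 17–19% |

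Choosing by Youden's J over all cut-offs raises the 48–50% to 65–67%.

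**Step 4: inflation with no association.** Searching all cut-offs lifts mean phi from 0.00 at 90 to about 0.24 at the best cut-off, with no real gain. The best cut-off reaches p < 0.05 (uncorrected chi-squared, either direction) in 22–27% of samples on the 19-point grid and 32–40% over all cut-offs, against about 5% at 90.

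**Step 5: inflation when 90 is truly best (80/80, all cut-offs).** In samples where another cut-off wins, phi appears to rise by 0.07 to 0.09. Applied to a large simulated population, the same cut-off changes phi by about −0.13, so it is worse than 90.

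**Step 6: when a lower cut-off really is better (all cut-offs).**
- True optimum 80: another cut-off wins in 91–95% of samples. Mean apparent gain is 0.14–0.18, real gain 0.02–0.07.
- True optimum 70: it wins in 97–99%. Mean apparent gain is 0.22–0.28, real gain 0.09–0.16.

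The overstatement runs from 0.278/0.163 = 1.7 times to 0.136/0.015 = about 9 times.

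**The case against.** The strongest defence is that this is an exploratory look in a study titled as a feasibility study, with the primary threshold fixed at 90 in section 9.2.1. That stands, and it limits the severity. Four stronger readings are tempting, and the documents do not support them.

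- **That the method cannot answer no.** It answers no whenever 90 is itself the best cut-off. On the 19-point grid, when 90 is truly best, that happens in 100 − 39 = 61% to 100 − 27 = 73% of samples. What cannot happen is a negative gain.
- **That the plan would make a false significance claim.** Section 9.3.3.2 states no hypothesis and attaches no p-value to the tuned cut-off. The 22–27% would matter only if one were quoted.
- **That a new cut-off would be carried into later work or care.** No section says so. Section 4.3 says only that the criterion could be explored and tuned.
- **That the primary result is compromised.** It is tested at 90 whatever the search finds. If there were no association, that test would usually be non-significant and the reader would see it.

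It is also fair to object that the rates rest on assumptions. Across three assumed score shapes on the 19-point grid, the rate under 80/80 ran from 24% to 38%, and nominal significance with no association from 18% to 28%. The direction is stable and the exact percentages are not.

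The exploratory label does not remove the bias. It excuses the lack of multiplicity control, but the method as written still gives an inflated answer to the question asked.

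**Conclusion.** The point holds for the exploratory analysis. The gain over 90 is selected and measured on the same subjects without correction, so it is never negative and is biased upward. That part is arithmetic, provided 90 is a candidate. The simulated rates are illustrations that depend on the assumed score distribution, metric and grid.

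A bare finding that a better cut-off exists says little. It arises in 92–93% of samples with no association on the 19-point grid, and over all cut-offs about as often with no association (about 97%) as when a lower cut-off really is better (91–99%). If the true optimum lies well below 90, the direction may be right, but the size of the gain is still overstated.

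Severity is low to moderate. This is a cheap improvement.

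**What to change.** In section 9.3.3.2:

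1. Name the association metric and a short list of candidate cut-offs that includes 90.
2. Report the association at 90 beside that at the best cut-off.
3. Report a bootstrap optimism-corrected gain. Repeat the whole search in each resample, then evaluate the cut-off selected there against 90 in the original or out-of-bag subjects. Optimism is the mean of (gain in the resample − gain of that same cut-off in the evaluation subjects), and the corrected gain is the apparent gain minus optimism. It can be negative. The original subjects are the more practical choice, since only about 30 × (29/30)^30 ≈ 11 subjects are out-of-bag per resample.
4. Report the spread of cut-offs selected across resamples.
5. If a p-value is quoted for the best cut-off, use a permutation p-value with the search repeated in each permutation.
6. Describe any new cut-off as hypothesis-generating until it is tested in a new sample.

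A rule that declares improvement when an interval for the gain excludes zero is not advisable. The searched gain is zero or more in every resample, so a simple percentile interval cannot fall below zero, and the study was sized only for the primary test.

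The cost is a paragraph in the plan and a short script, with no new data or subjects. The association reported at the tuned cut-off will look less favourable, and with about 30 subjects the corrected gain will be imprecise.

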
 Evaluate the correlation of testable parameters with sentence score at 1-day in quiet and at 1-month in noise. Evaluate the correlation of testable parameters, sentence scores and self-reported performance (SSQ12) at time of non-opposition. Determine whether shifting the good/poor performer 90% cut-off score would improve the correlation with pass/fail on the parameter tests. Explore the relationships between testable parameters measured post-implantation and demographic and hearing-related factors. 	
 Sentence recognition score in quiet with CI alone at 1-day. Sentence recognition with CI alone at 1-month: scores in quiet and in fixed levels of noise 10 dB & 5 dB SNR, or SNR50. Sentence recognition at one month near time of inclusion: scores in quiet and in fixed levels of noise 10 dB & 5 dB SNR, or SNR50. SSQ12 score at time of inclusion.

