3 SCHEDULE OF EVENTS

Visit Type	Screening	Inclusion	Collection	EOS
Timing of Investigation	NA	Day 0	Day 0	Month 1
Visit window (\pm)	NA		± 30 days	± 30 days
Procedures			retrospective	prospective
Written information and non-opposition form		X		
Demographics			X	
Eligibility	X			
Inclusion and exclusion criteria			X	
Hearing history (incl. preop audiogram and speech recognition)			X	
Medical, imaging and surgical history			X	
Collect CDX CustomSound device data file: Fitting parameters, NRT, Data logging			X	
Functional cognitive test scores and completion times (MoCA, Stroop, ÉCLA-16+ subtests)			X	
Sound field aided thresholds (1-day to 1-month)			X	
MBAA2 sentence recognition in quiet score at 1-day			X	
MBAA2 sentence recognition in quiet score at 1-month			X	
MBAA2 sentence recognition at 10 dB SNR score at 1-month (or verify as zero)			X	
MBAA2 sentence recognition at 5 dB SNR score at 1-month (or verify as zero)			X	
MBAA sentence recognition SNR50 at 1-month (or verify non convergent or score in quiet <80)			X	
Post-operative events related to the surgery or related to the device.			X	
Patient questionnaire (including SSQ12)				X

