4.3 Study Rationale

In the last 2-3 years routine clinical evaluation of adult CI recipients with tests of top-down and bottom-up processing parameters has been undertaken in Toulouse. This provides us with the opportunity to determine whether they are related to speech recognition performance. The centre also has consistent collection of sentence recognition scores after cochlear implantation (as seen in their publications). These two sets of data from the same patient population allow us to test the hypothesis that sentence recognition scores are influenced by a certain set of testable limiting factors which are generally cited in the literature. Furthermore, the definition of “poor” performance has also been established for this centre using the MBAA sentence recognition test. The use of the $\geq 90/100$ as a criterion is debateable but, as outlined in the previous section, is based upon the idea that 90/100 is the minimum expected outcome in the absence of limiting factors.

The results of the top-down and bottom-up processing parameter tests can all be mapped to a pass/fail outcome. The novelty then in the design of this study is to understand whether each limiting factor contributes to the good/poor performer status categorised using the sentence recognition test at 1 month. This contrasts with other methods which aim to develop a continuous outcome model where, for example, an expected speech recognition score can be generated and compared to an actual speech recognition score.

Some recent work within Cochlear has shown also large variability in subjective outcomes with CI measured via the SSQ12 even in the longer term (one to six years). Therefore, we include self-assessment of hearing performance outcomes by the CI recipient using the SSQ12. As outlined in the previous section, sentence recognition at 1-day could also be associated with the outcomes of the processing tests; with the assumption that listening experience during the first month after activation may influence the growth in sentence recognition score, and in the longer term. Thus, scores can also be collected for the period following 1-month, up until 1-2 years as available. This would allow us to investigate the trajectory of speech recognition learning with the CI and relate it to subjective performance at the time of data collection.

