7.3.3.6 Post-operative audiometric data

Aided sound-field warble-tone thresholds (dB HL: 250, 500, 1000, 2000, 4000 Hz) performed soon after activation will be collected.

The Toulouse centre presents sentence material at 65 dB SPL in quiet and in 8-talker babble presented in front from the same speaker. French MBAA2 sentence recognition scores (/100, single list per condition) will be collected for the implant ear alone where performed:

- In quiet at 1-day
- In quiet at 1-month
- 10 dB SNR at 1-month (or verify as zero)
- 5 dB SNR at 1-month (or verify as zero)

French MBAA dB SNR50 at 1-month (or verify non-convergent or score in quiet <80/100) will be collected. The SNR50 is derived from several fixed-SNR test scores using logistic interpolation.

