7.3.3.7 Long-term sentence recognition scores (up until time of recruitment)

French MBAA sentence recognition scores in quiet and in noise the implant ear alone will be collected where performed between one-month post-activation and the time of recruitment. Logistic interpolation may be used to obtain scores for missing test levels or SNR50 (data analysis stage). Dates of tests will also be collected to enable longitudinal extrapolation.

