9.2.3 Exploratory Endpoints

- Sentence recognition score at 1-day in quiet.
- SSQ12 score at time of inclusion.
- Sentence recognition score at 1-month: In quiet and in fixed levels of babble 10 dB & 5 dB SNR, and SNR50.
- Score/s at 1-day, 1-month, and later time points post activation up until the time of recruitment for various fixed SNRs.

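### Does the exploratory SSQ12-SNR50 correlation need a fixed visit and a rule for subjects without a numeric SNR50?

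*Combined protocol and SAP*

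**What the plan says.** The hypothesis in section 9.3.3.4 is that "there is a significant relationship between SSQ12 score and SNR50 for sentence recognition in noise". SSQ12 is answered at inclusion. The visit for SNR50 has to be found elsewhere:

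- Section 9.2.3 lists "Sentence recognition score at 1-month: In quiet and in fixed levels of babble 10 dB & 5 dB SNR, and SNR50". Its last item adds scores at later time points, up to recruitment, at various fixed SNRs.
- The synopsis has a 1-month endpoint and then a separate one, "Sentence recognition at one month near time of inclusion", which also covers SNR50.
- Section 4.3 wants the learning trajectory in order to "relate it to subjective performance at the time of data collection".
- Section 6.2 sets the objective "Evaluate the correlation of testable parameters, sentence scores and self-reported performance (SSQ12) at time of non-opposition".
- Section 7.3.3.7 collects scores and test dates up to recruitment and adds: "Logistic interpolation may be used to obtain scores for missing test levels or SNR50 (data analysis stage").

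On missing numbers, section 7.3.3.6 collects the 1-month SNR50 with the allowance "or verify non-convergent or score in quiet <80/100". The Schedule of Events has the same entry: "MBAA sentence recognition SNR50 at 1-month (or verify non convergent or score in quiet <80"). Section 9.1 puts every analysis on the full data set, sends missing scores to the study team and interpolates missing fixed SNRs. Section 9.8 allows parametric or non-parametric correlation, or linear models.

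**The concern.** Two things are left open. First, SSQ12 describes hearing at inclusion, while the SNR50 named outright in section 9.2.3 dates from 1 month after activation. For many subjects these are more than a year apart, so a 1-month pairing would blur the relationship.

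Second, a subject recorded only as non-convergent or under 80/100 has no number to correlate. Dropping such subjects is not a neutral loss. A quiet score under 80 is also under the 90 cut-off for a good performer, so that route removes poor performers only. The correlation would then rest on a small, range-restricted group of better performers. Leaving visit and handling open also means that both could be chosen after the data are seen.

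**Working it through.** **1. The plan's own power figure.** The only stated power is above 80% for the primary 2×2 test (section 9.4). Inputs: N = 30, sensitivity and specificity about 80% (section 7.2.3), alpha 0.05 (section 9.3.1). Exact binomial enumeration of the table gives:

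| Good/poor split | Chi-squared | Fisher |
|---|---|---|
| 50/50 | 0.94 | 0.87-0.89 |
| 40/60 | 0.93-0.94 | 0.88-0.89 |

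(Ranges cover fixed and random margins.) The claim reproduces. It uses good/poor status and battery pass/fail, not SNR50 or SSQ12, so it is untouched by this point. No power is claimed for section 9.3.3.4.

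**2. Time gap.** Recruitment works back from the last 2021 implant (section 7.2.5) at about 25 eligible implants a year (section 7.1.1). For 30 subjects: 30/25 = 1.20 years, about 14 months. For the first draw of 30 × 1.2 = 36: 36/25 = 1.44 years, about 17 months.

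**3. Who could be lost at 1 month.** Section 4.2.2 expects 30-50% to reach 90, and 16/61 = 26% exceeded it in the earlier sequence. These are lower bounds on the number scoring 80 or more:

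- 30 × 16/61 = 7.9
- 30 × 0.30 = 9
- 30 × 0.50 = 15

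If the earlier median of about 72 holds, at most half (15 of 30) reach 80. The documents do not give the share itself. A non-convergent subject with a quiet score of 80 or more need not be a poor performer, so only the under-80 route is certain to select.

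**4. Cost of the worst reading.** Assumptions not in the documents: true correlation 0.5 between SSQ12 and noise performance, normal latent scores, Spearman test, two-sided 0.05. With all 30 values, power is about 0.77 and mean Spearman 0.47. If quiet and noise performance rank subjects identically and 15 are dropped, power is about 0.20 and mean Spearman 0.29. Timing alone, with nobody missing: if 1-month and later noise performance correlate 0.6-0.9, power with the 1-month value is 0.32-0.69.

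**5. Would a worst-rank rule repair it?** All 30 are kept, with those lacking an SNR50 tied at the bottom. The power columns are for 50% measurable; mean Spearman covers 30-50% measurable.

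| Quiet-noise correlation | Power, numeric only | Power, worst rank | Mean Spearman, numeric only | Mean Spearman, worst rank |
|---|---|---|---|---|
| 1.0 | 0.19 | 0.69 | 0.24-0.29 | 0.38-0.43 |
| 0.7 | 0.34 | 0.52 | 0.37-0.40 | 0.29-0.36 |
| 0.5 | 0.39 | 0.36 | 0.40-0.43 | 0.22-0.29 |

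Against 0.47 with no loss, the rule helps at the top of the table and harms the estimate at the bottom. At a later visit with an assumed 70-90% measurable and quiet-noise correlation 0.5, power is 0.54-0.72 with worst rank and 0.56-0.70 on numeric values: no gain.

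**6. What the plan leads an analyst to do.** The loss in step 4 needs two choices together: the 1-month value, and deletion of anyone without a number.

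- *Visit.* The synopsis already lists 1-month scores before it lists those near inclusion. The second entry therefore only makes sense as a later measurement, and its stray reference to one month reads as a slip. Sections 4.3, 6.2 and 7.3.3.7 and the last item of section 9.2.3 agree. SNR50 is derived from fixed-SNR scores (section 7.3.3.6), so the later inputs are in section 9.
- *Handling.* Section 9.1 requires the full data set, interpolates missing SNRs and fits longitudinal scores to a schedule out to 3 years. It labels these secondary endpoints although there are none, which is a clerical slip. The status entries record why a number is absent; nothing says that they exclude the subject.

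**The case for a change.** The strongest case for a change is that this is a named hypothesis whose sibling in section 9.3.3.1 gives visits for its sentence scores, so naming one is the protocol's own practice. The text in section 9.1 does not fully close the second gap either. Its example of assuming a zero concerns sentence scores, whereas 0 dB is a real SNR50 and not a floor value. Interpolation cannot be relied on for a non-convergent subject or one far below 50% correct. A few sentences would settle both points, and the status, scores and dates are already collected.

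All of that stands as a description of what is unwritten. It does not show that the plan leads to a wrong analysis. Pairing SSQ12 with the nearest available SNR50, deriving it from fixed-SNR scores where possible and reporting how many subjects had only a status is what a competent analyst would do from the existing text. The one element that goes beyond this, worst rank as the main analysis, is not clearly better (step 5). It also needs a separate rule for subjects who fail to converge at ceiling.

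**Conclusion.** The gaps exist, but they are missing detail in one exploratory, unpowered correlation in a 30-subject feasibility study. The fall in power from about 0.77 to about 0.20 holds only if the 1-month value is used on numeric cases alone, half the subjects have no number, the true correlation is 0.5, and quiet and noise scores rank subjects identically. The plan makes neither of the first two choices, and the last three figures are assumptions. The real share under 80/100, and the share without an SNR50 at a later visit, cannot be worked out from the documents. Even with pairing in time and nobody missing, power is about 0.77, so a null result would remain inconclusive however the rule is written. The primary 2×2 test and its stated power are unaffected. No change to the plan follows; in reading the result, look for the visit used and the number of status-only subjects.
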